**2.21 Will this research study be conducted within a nursing home located in Pennsylvania?**

\* No

[reviewer notes-]

## Section 3 - Human Subjects

### 3.1 What is the age range of the subject population?

5 to 18 years old

### 3.2 What is their gender?

\* Both males and females

Provide a justification if single gender selected:

### 3.3 Will any racial or ethnic subgroups be explicitly excluded from participation?

\* No

If **Yes**, identify subgroups and provide a justification:

### 3.4 For studies conducted in the U.S., do you expect that all subjects will be able to comprehend English?

\* Yes

[reviewer notes-]

### 3.5 **Participation of Children:** Will children less than 18 years of age be studied?

\* Yes

#### 3.5.1 Specify the age range of the children to be studied.

(Check all that apply below:)

\*

Choices

0-6 years of age

7-13 years of age

14-17 years of age

#### 3.5.2 Provide a rationale for the specific age ranges of the children to be studied:

Child needs to be adequately potty trained with daytime dryness and be able to communicate quality of life subjective information to parents.

#### 3.5.3 Describe the expertise of the study team for conducting research with children within this age range:

The study team has significant clinical experience in the pediatric population as Drs. [name], [name], [name], and [name] are board certified urologic pediatricians and have

facilitated a number of research studies through the Children's Hospital of Pittsburgh urology department.

- 3.5.3.1 Have you obtained the following clearances from all research staff who may have direct contact with children under the age of 18? Direct contact under the law includes face-to-face, and telephonic or electronic, contact with minors. Please see the [Child Clearances](#) guidance document for further explanation?**

**Pennsylvania Department of Public Welfare Child Abuse History Clearance; Pennsylvania State Police Criminal Record Check; and FBI Criminal Background Check**

**Yes**

**Note:** If No, once all clearances are obtained, a modification must be submitted.

**If you selected N/A, please explain:**

It is important to note that "direct contact" refers not only to face-to-face meetings but also extends to communication via phone (including text messaging), social media or internet. Direct contact also includes the care, guidance, supervision or control, or routine interaction with, minors. Conversely, a participating investigator or support staff member who does not have direct contact, either electronically or in person, with children does not need to obtain clearances (e.g., statistician, non-clinical laboratory personnel, etc.). If your research study provides babysitting services, the babysitters must have the required child clearances.

**\* Note:** It is the **responsibility of the principal investigator** to ensure that all research staff have these clearances prior to any interaction with children. Contact Human Resources at [contact] for assistance with this process.

- 3.5.4 Describe the adequacy of the research facilities to accommodate children within this age range:\***  
Addressed below:

The department of urology at the Children's Hospital of Pittsburgh outpatient clinic has all of the necessary resources to implement this research study.

- 3.5.5 Permitted Categories of Research: The Federal Policy and FDA regulations governing human subject protections specify that research involving children must fall into one of the following permitted categories.**

\*

The research does not involve greater than minimal risk [45 CFR 46.404/21 CFR 50.51].

#### **45 CFR 46.406**

- The risk represents only a minor increase over minimal risk.
- The research procedures present experiences to the subjects that are reasonably commensurate with those inherent in their actual or expected medical, dental, psychological, social, or educational situations.

- The research procedures are likely to yield generalizable knowledge about the subjects' disorder or condition which is of vital importance for understanding or amelioration of the subjects' disorder or condition.

**45 CFR 46.407**

- The risk is justified by the anticipated benefit to the subjects; and the relation of the anticipated benefit to the risk is at least as favorable to the subjects as that presented by available alternative approaches.

Provide a justification which **must address all considerations** related to the designated category of research:

At stated prior we feel this study provided minimal risk based on the rarity and minority of side effects from previous TENS studies in adults. We will use a voltage only high enough to elicit an involuntary twitch of the toes, which is generally non-painful.

Although the electrical stimulation may help subjects with nocturnal enuresis, this benefit is not known or guaranteed. However, information learned from this study will help investigators learn how to better treat children with nocturnal enuresis in the future.

[\[reviewer notes-\]](#)

**3.6 Does this research study involve prisoners, or is it anticipated that the research study may involve prisoners?**

\* No

[\[reviewer notes-\]](#)

**3.7 Will pregnant women be knowingly and purposely included in this research study?**

\* No

[\[reviewer notes-\]](#)

**3.8 Does this research study involve neonates of uncertain viability or nonviable neonates?**

\* No

[\[reviewer notes-\]](#)

**3.9 Fetal Tissues: Does this research involve the use of fetal tissues or organs?**

\* No

[\[reviewer notes~\]](#)

--->

**3.10 What is the total number of subjects to be studied at this site, including subjects to be screened for eligibility?**

Note: The number below is calculated by summing the data entered in question 3.11. Any additions or changes to the values entered in 3.11 will be reflected in 3.10.

\* 40

**3.11 Identify each of the disease or condition specific subgroups (include healthy volunteers, if applicable) that will be studied.**

Click on the "Add" button and specify for each subgroup:

1) how many subjects will undergo research related procedures at this site; and

2) if applicable, how many subjects will be required to undergo screening procedures (e.g., blood work, EKG, x-rays, etc.) to establish eligibility. **Do Not include subjects who will undergo preliminary telephone screening.**

\*

Subgroup	Number to undergo research procedures	Number to undergo screening procedures
View Pilot study of tibial nerve stimulation	25	40

**3.12 Provide a statistical justification for the total number of subjects to be enrolled into this research study at the multicenter sites or this site.**

\* Described below:

This is a pilot study to determine if foot stimulation has any effect on nocturnal enuresis. The study is designed through the use of an objective night-time voiding log and subjective quality of life questionnaires to determine the effect of foot stimulation. As the variations on these symptom parameters is unknown, it is difficult to to determine the total number of subjects based on statistical analysis. Therefore, we decided on 25 subjects in this pilot study. Once statistical significance is reached , we will stop recruiting additional subjects in order to maintain the subject number at a minimum.

[\[reviewer notes~\]](#)

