hour before bed for 2 weeks to 25 subjects. Subjects will be required to keep a daily log indicating the number of night-time incontinent voids. Subjects will also be asked to complete a validated questionnaire prior to treatment, during the two week treatment phase and two weeks after treatment. The primary outcomes of this study are improvement in the average number of night-time incontinent voids measured by daily log and subjective symptom improvement based on questionnaire comparison at the three phases of the study. Subjects who feel they are having a positive response to TENS treatment and would like to continue participation in the study for an additional 6 weeks may do so.

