#### Questionnaire:

Subjects will complete the quality of life questionnaire attached to this application at the start of the study (prior to week 1) to establish a baseline, after the second week of treatment period (week 4 of study) to determine a treatment effect, and after the sixth week to determine any residual post-treatment effect.

The subjects can call or email the investigators anytime during the 6-week at-home test for questions or any problems encountered. At the end of the 6-week study, the subjects are asked to return the stimulator and night-time voiding log to the investigator's office.

Subjects who feel they are having a positive response to TENS treatment and would like to continue participation in the study for an additional 6 weeks may do so. We will ask that they continue to keep their logs and answer the questionnaires

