**2.18 Describe the statistical approaches that will be used to analyze the study data.**

\* Addressed below:

The data will be statistically analyzed using student t-test and ANOVA

[\[reviewer notes~\]](#)

**2.19 Will this research be conducted in (a) a foreign country and/or (b) at a site (e.g., Navajo Nation) where the cultural background of the subject population differs substantially from that of Pittsburgh and its surrounding communities?**

\* No

Note that copies of training records, licenses, certificates should be maintained in the study regulatory binder and are subject to audit by the Research Conduct and Compliance Office (RCCO).

In addition, individuals planning to conduct human subject research outside the United States must complete an optional module on the CITI training website: International Studies. [Click here](#) to access the instruction sheet for accessing optional CITI modules.

[\[reviewer notes~\]](#)

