3. The investigators will monitor the progress of the study and the efficacy of the treatment after collecting data from the first 10 subjects. Any unexpected adverse effect will be addressed immediately and reported to the IRB committee. In addition to the monitoring of every 10 subjects, an annual review of the study will also be conducted to assure the experimental design, identify any unexpected adverse effects for reporting, and review the progress of subject recruitment

4. The data will be locked in the urology office by the investigators for safety and privacy. An annual review of the safety and privacy of the data will be performed. If any problem occurs, it will also be addressed immediately during any time of the year.

5. The following will be reported to IRB annually: a list of persons who monitored the data

and safety; the date when the monitoring/review occurs; a summary of any problems detected; final decisions about changes of the study based on the annual review.

6. The potential adverse events may be reported to IRB including:

Use of TENS stimulator: Foot skin irritation, redness, or rash, or foot cramp.

[reviewer notes~]

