The information linking the ID number with the subject's name will be stored in a separate secure location during the study, and will be destroyed at the end of the study. We will not keep any document to link the subject's name to the ID number. After the study is finished, we will have consent forms with subjects names and data forms with ID numbers. Since the link between names and ID numbers are not kept, there will be no identifiable information that could be released. However, the data on papers will still be locked for safety reasons and the electronic data will be stored in password-protected, fire-walled computers.

- 5.16 If the subject withdraws from the study, describe what, if anything, will happen to the subject's research data or biological specimens.**

If a subject requests withdrawal or is withdrawn by the PI, no further data should be collected, but all data obtained prior to withdraw will be retained and analyzed for the study purposes.

- 5.17 Following the required data retention period, describe the procedures utilized to protect subject confidentiality.** (e.g., destruction of research records; removal of identifiers; destruction of linkage code information; secured long-term retention)

After the required data retention period, all data and subject information will be destroyed.

[\[reviewer notes-\]](#)

**6.1 Will research subjects or their insurance providers be charged for any of the procedures (e.g., screening procedures, research procedures, follow-up procedures) performed for the purpose of this research study?**

\*  
No

[\[reviewer notes-\]](#)

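### Section 3.12 stops recruitment once a result is significant, with no alpha, boundary or named outcome, so a nominal 5% test can carry a false-positive rate of up to about 10%

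*Combined protocol and SAP*

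**What the plan says.** Section 3.12 says that the variability of the outcomes is unknown and that the sample size could therefore not be derived: "Therefore, we decided on 25 subjects in this pilot study". It then makes a test result the trigger for ending recruitment: "Once statistical significance is reached , we will stop recruiting additional subjects in order to maintain the subject number at a minimum".

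The whole analysis section (2.18) reads: "The data will be statistically analyzed using student t-test and ANOVA". It gives no significance level, no sidedness, and no link between test and outcome. Section 2.3 describes a single-arm, open-label comparison within the same child.

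Two parts of the data and safety monitoring plan (5.13, item 3) bear on timing: "The investigators will monitor the progress of the study and the efficacy of the treatment after collecting data from the first 10 subjects", and "In addition to the monitoring of every 10 subjects, an annual review of the study will also be conducted". Neither mentions a significance test, a threshold or the rule in 3.12.

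The abstract (CS2.1) names two primary outcomes: "The primary outcomes of this study are improvement in the average number of night-time incontinent voids measured by daily log and subjective symptom improvement", the latter by questionnaire. Section 3.12 does not say which of them triggers the stop, or which of the three study phases are compared.

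On data flow, section 2.6 (Questionnaire) says: "At the end of the 6-week study, the subjects are asked to return the stimulator and night-time voiding log". Children can therefore be mid-study when a test is run. No section says whether the triggering test, or a later test on everyone enrolled, is the study's result.

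**The concern.** If significance decides when recruitment ends, the data must be tested before all 25 children are in, possibly several times. Each unadjusted test is another chance of a false positive, and a trial that stops on one has fewer later children to correct it. A p-value below 0.05 reached this way need not mean a 5% error rate.

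The estimate is affected too. Trials that happen to run high stop early and trials that run low continue, so with a true effect the average estimate is too large. That matters here because the variability is said to be unknown: an estimate of the effect and its SD is a main product of this pilot, and there is no concurrent control.

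**Working it through.** **The plan's own figure.** The 25 cannot be reproduced, because 3.12 gives no effect size, SD, alpha or power. For orientation only, a paired t-test at two-sided 0.05 with n = 25 has 80% power for a change of 0.58 SD.

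**Inputs.**
- From the documents: maximum n = 25 (3.12); same-child comparison (2.3); a first efficacy review at 10 children and a mention of every 10 (5.13).
- Assumed: two-sided 0.05 at each test, one outcome, tests at 10, 20 and 25, and stopping for significance in either direction.
- Not given, so varied: *m*, the number of children already enrolled at the trigger whose data are added before the final test.

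**Rule as simulated.** Let D be the within-child change and T(n) = mean(D) / (s/√n). At n = 10 and n = 20, stop if |T(n)| exceeds the 0.975 quantile of t with n − 1 degrees of freedom. After a stop, the final test uses min(n + m, 25) children; for m > 0 only that updated test counts. Otherwise test at 25.

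**Where the excess comes from (m = 0, no effect).** The test at 10 rejects in 5.0% of trials. By 20, 8.5% have rejected at least once, so the second test adds 8.5 − 5.0 = 3.5 points. By 25 it is 10.4%, so the last adds 10.4 − 8.5 = 1.9 points. A single test at 25 gives 5.0%.

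**False-positive rate by number added and by test schedule (Monte Carlo):**

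| Children added (m) | Tests at 10/20/25 | Tests at 10/25 | Test after every child from 10 |
|---|---|---|---|
| 0 | 10.4% | 8.8% | 15.6% |
| 1 | 8.1% | 7.3% | 10.1% |
| 2 | 7.2% | 6.7% | 8.6% |
| 5 | 5.9% | 5.9% | 6.6% |
| 10 | 5.3% | 5.3% | 5.4% |
| 15 | 5.0% | 5.0% | 5.0% |

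From m = 5 the test at 20 no longer matters, since 20 + 5 = 25. At m = 15 all 25 are enrolled before the first test (10 + 15 = 25) and the rule does nothing.

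**Other readings, tests at 10/20/25.**
- Only a significant benefit stops recruitment, final test two-sided: about 7.7% (m = 0) to 5.4% (m = 5). The estimate under no effect is then biased by about +0.01 SD or less.
- Repeated-measures ANOVA over the three phases: 10.6% (m = 0) to 6.0% (m = 5). Paired t-test on wet-night counts out of 14: 10.2% to 5.8%.
- Unpaired t-test, m = 0: 4.7% at a within-child correlation of 0.3 and 1.9% at 0.5. A single unpaired test at 25 gives 2.1% and 0.7%, so the repeated tests still more than double the rate.

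**Bias with a true effect, either-direction stopping.** A true 0.5 SD averages 0.56 (m = 0) to 0.53 (m = 5); a true 0.3 SD averages 0.34 to 0.32. One test at a fixed 25 averages 0.50 and 0.30.

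**Check of boundaries.** Nominal two-sided levels of 0.0012, 0.0218 and 0.0402 at 10, 20 and 25 give an overall error of 4.8%. A constant 0.022 gives 4.9%. If two to five enrolled children are added and the updated test is judged at the last level, the error falls to 4.4–4.1% and 3.3–2.6%, so both stay below 5%.

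**The case against.** The strongest reply is that the size is not established. Alpha, the tests and the overrun are all assumed. Six-week follow-up with logs returned at the end makes a large overrun possible, and with ten children added the rate is only 5.3%. A reader might infer that the error rate exceeds 5% whichever children are analysed. The documents do not support that: about 6% is not a floor, and with all 25 enrolled before the first test there is no inflation. This limits the size of the problem but does not defend the rule. Either it shortens recruitment and raises the error rate, or it has no effect and can be deleted.

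Other replies stand in part:
- Section 5.13 does not say that a significance test is run at the ten-child reviews. Treating 10/20/25 as the plan's interim schedule is an inference.
- Section 5.16 says that "all data obtained prior to withdraw will be retained and analyzed for the study purposes". A reader might take this to mean that everyone enrolled is analysed. It concerns withdrawn subjects and does not settle what happens to children in follow-up when recruitment stops.
- Section 2.18 does not say that the t-test is paired, and an unpaired test would be conservative at moderate within-child correlation. Section 2.3 makes the paired reading the natural one.
- The abstract speaks of improvement, so stopping for benefit only is plausible and lowers the upper figure to about 7.7%.
- With two primary outcomes and either allowed to trigger, the rate with none added is 16–20%. This should not be charged to the stopping rule alone: a single test of each at 25 already gives about 8–10% from ordinary multiplicity.

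That the study is a pilot does not answer the point. Section 3.12 itself makes significance an operative decision, and the abstract names primary outcomes.

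**Conclusion.** The concern holds. Section 3.12 is uncorrected optional stopping, and nothing elsewhere supplies an alpha, a boundary, a correction, a trigger outcome or a schedule of tests tied to the rule. Under the stated assumptions, with tests at 10, 20 and 25, the false-positive rate for one outcome lies between 5% and about 10%. The overrun decides where in that range it falls, and the plan does not let us determine it. More frequent testing would be worse, up to 15.6% if every child from the tenth triggers a test and none are added. When the rule does shorten the trial, a moderate true effect is overstated on average by a few hundredths of an SD. The defect in the wording is certain; its size depends on the assumptions. It should be fixed before any efficacy test is run, because the rule cannot be repaired once results have been seen.

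**What to change.** **Preferred.** Delete the sentence in 3.12 that stops recruitment on significance, enrol the planned 25 and test once at the end. Keep the ten-child reviews in 5.13 for safety and progress, and state that no recruitment decision rests on efficacy significance. In 2.18, name the alpha, the test (paired) and the one outcome and comparison it applies to, for example the night-time log count in the stimulation weeks against baseline.

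**Alternative.** Keep early stopping, but state a group-sequential boundary at 10, 20 and 25, for example nominal two-sided p of about 0.001, 0.022 and 0.040. State that all enrolled children are followed and enter the final analysis, and name the outcome and comparison in the same way.

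**Cost.** Wording only; the maximum of 25 is unchanged. The price is fewer early stops. At a true 0.5 SD the present rule enrols a mean of about 19 children with none added and about 22 with five added, against 25 under the preferred fix.

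Power at 0.5 SD:

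| Design | None added | With overrun |
|---|---|---|
| Present rule | 72% (with 10.4% error) | 65–67% (1–5 added) |
| Single test at 25 | 67% | not applicable |
| Boundary 0.001/0.022/0.040 | 65% | 63–64% (2–5 added) |
| Constant 0.022 | 58% | about 52% (2–5 added) |

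With any overrun counted, a single test at 25 gives up essentially no power. If early stopping is kept, the constant level is the costlier boundary, and the overrun column is the one to plan on, since all enrolled children enter the analysis.

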**3.13 Inclusion Criteria: List the specific criteria for inclusion of potential subjects.**

1. Children ages 5 to 16 years old without any specific neurological disorder or urinary tract infection, clinically diagnosed as having nocturnal enuresis AT LEAST 4 episodes per month by history

2. Currently having no daytime overactive bladder symptoms, i.e. urinary frequency,

urgency, or daytime incontinence

3. Having been assessed for and treated if applicable for behavioral etiologies of nocturnal enuresis - consuming excess fluids or specific bladder irritants

4. Having been assessed for and treated if applicable for constipation

**3.14 Exclusion Criteria: List the specific criteria for exclusion of potential subjects from participation.**

1. Children with known neurological disorders which may be contributing to nocturnal enuresis episodes

2. Children found through history to have significant behavioral causes of nocturnal enuresis including consumption of excessive fluids or known bladder irritants

3. Children with chronic constipation who are non-compliant with previous pharmacologic efforts to treat.

4. Children who are not adequately potty trained

5. Children with significant daytime symptoms of overactive bladder including frequency, urgency, and daytime incontinence

5. Children who do not tolerate initial stimulation training session in the urology clinic upon enrollment

6. Children with any implantable medical devices such as a pacemaker will be excluded from the study

Note: Any patient currently taking medication such as an anti-muscarinic or a tricyclic antidepressant for overactive bladder at time of enrollment will be eligible to participate and will be continued on their usual medication and dosage throughout the study.

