**CS2.0 Title of Research Study:**

**Foot Neuromodulation for Nocturnal Enuresis in Children**

**CS2.0.1**

**Requested approval letter wording:**

**CS2.1 Research Protocol Abstract:**

Background: Previous animal model studies at the University of Pittsburgh have shown a significant impact on inhibiting bladder overactivity and increasing bladder capacity with neuromodulation techniques, specifically tibial nerve stimulation. This has been translated into adult clinical trials through the department of urology. Through the use of a commercially available subcutaneous nerve stimulator placed on the dorsum of the foot, we were able to demonstrate a significant increase in bladder capacity and the delay of voiding sensation for up to 5 hours after stimulation in eight healthy subjects. This prompted the clinical trial approved under IRB PRO13020474 which is currently enrolling patients.

The incidence of night-time overactive bladder leading to nocturnal enuresis (bedwetting) is very common in the pediatric and teenage population, particularly in patients without daytime bladder overactivity symptoms. When behavioral modification (i.e. refraining from night-time fluid consumption and bladder irritants, and bedwetting alarms for timed voiding) fails which it often does there is a paucity of effective and safe treatment options. Medications can be tried, but generally these are from the tricyclic antidepressant family and carry significant side effects limiting their use.

Aim: We aim to utilize the same technology currently being studied under IRB PRO13020474 for pediatric patients with nocturnal enuresis, taking advantage of the possible increase in bladder capacity and inhibited bladder activity to potentially help children stay dry at night. Electrical stimulation will be applied to the foot via skin surface electrodes for a minimum of 1

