**2.3 Summarize the general classification (e.g., descriptive, experimental) and methodological design (e.g., observational, cross-sectional, longitudinal, randomized, open-label single-blind, double-blind, placebo-controlled, active treatment controlled, parallel arm, cross-over arm) of the proposed research study, as applicable.**

This is an experimental, open-label study. Both the subject and the investigator will be informed about the foot stimulation. The results obtained before and after the treatment will be compared in the same subject.

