**2.3.1 Does this research study involve a placebo-controlled arm?**

\* No

[\[reviewer notes-\]](#)

**2.4 Will any research subjects be withdrawn from known effective therapy for the purpose of participating in this research study?**

\* No

[\[reviewer notes-\]](#)

**2.5 Will screening procedures (i.e., procedures to determine research subject eligibility) be performed specifically for the purpose of this research study?**

\* Yes

**2.5.1 List the **screening** procedures that will be performed for the purpose of this research study. Do NOT include the inclusion/exclusion criteria in this section as they will be addressed in section 3; questions 3.13 and 3.14.**

The screening procedure only includes a review of patient's medical records and performing an office based urinalysis to rule out concern for urinary tract infection. No other procedures will be performed. Patient's medical record has all the information we need to determine the idiopathic nocturnal enuresis condition. A urinalysis is normally done as part of standard of care for all office visits. The standard office visit questions, which is also available in the medical record and includes questions about neurological disorders, spinal cord injuries, and so forth will be used to rule out those who may have a neurological reason for nocturnal enuresis. Drs. [name], [name], [name], and [name] who have clinical responsibilities to the patient will review the medical records for eligibility. We also request a waive of consent for this review on section 4.7.

[reviewer notes~]

**2.6 Provide a detailed description of all research activities (e.g., all drugs or devices; psychosocial interventions or measures) that will be performed for the purpose of this research study.**

This description of activities should be complete and of sufficient detail to permit an assessment of associated risks.

At a minimum the description should include:

- **all research activities**
- **personnel (by role) performing the procedures**
- **location of procedures**
- **duration of procedures**
- **timeline of study procedures**

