**Night-time voiding log:**

The subject/parents will be instructed to record a night-time voiding log specifying the number of incontinent episodes per night. This log is included in the IRB application. Subjects/parents will fill out the log for a two week period prior to foot stimulation to determine a baseline average of nocturnal enuresis episodes, during the two week foot stimulation period to measure any acute effect on nocturnal enuresis episodes and finally during the two weeks after stimulation to evaluate any post-stimulation residual benefit.

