**Neuromodulation:**

In the office to calibrate TENS device - skin surface electrodes will be attached to the bottom of one foot for electrical stimulation. The stimulator and electrodes are FDA-approved devices for TRANSCUTANEOUS ELECTRICAL NERVE STIMULATION (TENS) and are commercially available. The stimulation characteristics include a continuous frequency of 5 Hz, pulsewidth 0.2 ms, and intensity 2-4 times the threshold voltage required for inducing

toe twitching - or the intensity that the subject feels comfortable with. The subjects will also be instructed how to use the stimulator and where to attach the electrodes on the foot at the beginning of the study. The investigator will provide the stimulator and electrodes. The subjects will be asked to wear socks to prevent the electrodes from detachment and to stop the stimulation during walking or in any non-resting situation. Subjects will be provided a TENS device and disposable foot pads for two weeks of treatment. Subjects will be asked to use the stimulator for a MINIMUM of 60 minutes in the evening prior to bedtime at home for two weeks. They will be encouraged to use the stimulator for more time than the minimum as long as they accurately record the total duration. Stimulation will be performed during the second and third weeks of the study only.

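### Changes in alarm use, evening fluids or medicine between the study windows are neither recorded, as far as the plan describes, nor allowed for in the analysis, so they could pass for a stimulation effect

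*Combined protocol and SAP*

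**What the plan says.** The Note to section 3.14 applies to "Any patient currently taking medication such as an anti-muscarinic or a tricyclic antidepressant for overactive bladder at time of enrollment". Such children are eligible and "will be continued on their usual medication and dosage throughout the study". It is silent on children who are not taking such a drug at entry, and on measures other than drugs.

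The abstract (CS2.1) and the background (1.3) list the usual behavioral measures against bedwetting as "refraining from night-time fluid consumption and bladder irritants, and bedwetting alarms for timed voiding", and go on to mention medication. Inclusion criteria 3 and 4 require that behavioral causes and constipation have been assessed and, where applicable, treated before entry.

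On data, section 2.6 tells families to "record a night-time voiding log specifying the number of incontinent episodes per night". Under Neuromodulation it also asks for the total stimulation time. On design, section 2.3 says "The results obtained before and after the treatment will be compared in the same subject", and section 2.3.1 answers No to a placebo arm. Section 2.17 compares the episode count in weeks 1-2, 3-4 and 5-6. Section 2.18 names a t-test and ANOVA, with no mention of other treatments.

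**The concern.** Each child serves as his or her own control. That removes whatever stays the same over the six weeks and nothing else. If some families start an alarm, cut evening drinks or begin a medicine in weeks 3-4, the fall in episodes is added to any effect of stimulation. If they do so in weeks 5-6, after the device has been stopped, it looks like the residual benefit that the third window is meant to detect. Abandoning a measure between windows would bias the comparison the other way.

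The 3.14 Note keeps one class of drug steady, which removes this problem for that class only. The other measures that the protocol itself treats as relevant to bedwetting are left open. If changes are not written down as they happen, the analyst can neither see them nor allow for them, and asking families afterwards is a poor substitute.

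**Working it through.** **Step 1. Is there any other rule?** The related provisions, side by side:

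| Place | What it covers | Fixes treatment after entry? |
|---|---|---|
| 3.14 Note | Overactive-bladder drugs already taken at enrollment | Yes, for those drugs |
| 2.4 | Whether children are taken off effective therapy in order to join (No) | No; does not address starting or changing one |
| 3.13, criteria 3-4 | Behavioral causes and constipation assessed and treated | No; entry only |
| 3.14, exclusions 2-3 | Excess fluids or irritants; constipation with non-compliance | No; entry only |
| CS2.1 and 1.3 | Alarms, fluids, irritants and medication as background | No |

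The Note stands alone. It is also limited to drugs for overactive bladder, whereas inclusion criterion 2 requires that the child has no current daytime overactive-bladder symptoms. A drug taken for the bedwetting itself is therefore not clearly covered.

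**Step 2. Would the data show a change?** As described in 2.6, the records hold episodes per night and stimulation duration. No field for other treatments is described.

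**Step 3. How large could the effect be?** The plan gives no SD, mean count or effect size, and section 3.12 says that the variation is unknown. There is no figure of the plan's to reproduce: its 25 subjects are chosen, not calculated. What follows rests on assumptions.

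- Assumed: stimulation does nothing; a quarter of families make one added change, all in the same window and in the helpful direction; it cuts episodes by 20% to 40%.
- Spurious mean shift = share of families × proportional cut × mean count per two weeks.
- At an assumed mean of 5 per two weeks: 0.25 × 0.20 × 5 = 0.25, and 0.25 × 0.40 × 5 = 0.50.
- At the entry minimum of 4 per month (criterion 1), about 2 per two weeks: 0.25 × 0.20 × 2 = 0.10, and 0.25 × 0.40 × 2 = 0.20.

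**Step 4. False-positive rate.** For a two-sided 5% paired t-test with n = 25 (24 degrees of freedom, critical value 2.064), the noncentrality is shift × √25 / SD of the difference. For example, a shift of 0.5 at SD 1.5 gives 0.5 × 5 / 1.5 = 1.67. The exact noncentral-t rejection probabilities are:

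| Shift (episodes) | SD 1.5 | SD 2.0 | SD 2.5 |
|---|---|---|---|
| 0.10 | 6.2% | 5.7% | 5.4% |
| 0.20 | 9.8% | 7.7% | 6.7% |
| 0.25 | 12.6% | 9.2% | 7.7% |
| 0.40 | 24.9% | 16.1% | 12.0% |
| 0.50 | 36.0% | 22.5% | 16.1% |

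The nominal rate is 5%. The range runs from negligible inflation to about seven times nominal (36.0 / 5 = 7.2), and the documents do not say where in it the trial would fall.

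**The case against.** The strongest case against has four parts.

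- **The weakness is disclosed.** This is a pilot, openly described as open-label and without a placebo arm, and co-treatment is one instance of what an uncontrolled design cannot separate. That is true. But this instance can be measured for almost nothing, which most of the others cannot.
- **Entry criteria narrow the room for change.** Fluids, irritants and constipation are dealt with before enrollment. This stands, most of all for fluids, and makes the larger shifts less plausible. It does not touch alarms or new medicines, and it sets no rule after entry.
- **The log form may already ask.** It is an attachment under 2.8 that was not available, and neither were the consent pages. The description in 2.6 is not shown to be complete. This stands, and the fix is conditional on it.
- **Every magnitude is assumed.** This stands too. The inflation is small at the entry minimum, and the table supposes that all changes fall in one direction and one window.

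A reader might infer more than the documents support. One inference is that families will tighten the evening routine in just the stimulation weeks; no section says so, and it is only plausible. Another is that the requirement "to stop the stimulation during walking or in any non-resting situation", together with at least 60 minutes' use before bed, makes the windows unequal through background care. That rest is part of the intervention as delivered, and recording other treatments would neither reveal nor remove its effect.

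**Conclusion.** The gap holds as a matter of recording and analysis. Background treatment after entry is fixed for one drug class only. Changes in alarm use, evening fluids or enuresis and bowel medicine are not among the data described, and a before-after comparison within the child cannot tell such a change from stimulation. Treatment that stays constant over all six weeks cancels out and does no harm.

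The size is unknown: about 5% to 36% false positives for shifts of 0.1 to 0.5 episodes, with SDs of the difference from 1.5 to 2.5, n = 25 and two-sided 5%. The conclusion does not depend on any one of these figures. It rests on the text of 3.14 and 2.6, and on the log form holding no field that 2.6 leaves out.

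A reader might go on to conclude that families should be told to hold these treatments fixed. That is a matter of clinical management for the sponsor and does not follow from this point.

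**What to change.** 1. Unless the form already has one, add to the night-time log a nightly tick, with the date, for any change in alarm use, evening fluids or medicine (enuresis or bowel).
2. Add to section 2.18 a sensitivity analysis of outcome 1, expressed as episodes per recorded night. A per-night rate is needed because outcome 1 is a two-week count, and dropping nights leaves windows of unequal length. State in advance which of two versions applies: leave out nights after a change or, for the weeks 3-4 comparison, leave out children with a change before the end of week 4. Report how many children and nights are lost.
3. State in 3.14 whether the Note's limit to overactive-bladder drugs taken at enrollment is intended.
4. Reconcile the stimulation weeks, since they define the windows: Neuromodulation (2.6) gives the second and third weeks, while 1.2 and 2.17 give the third and fourth.

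The cost is a small logging burden and one extra analysis. The loss of data in that analysis may not be small: a change from night 15 on would remove 28 of a child's 42 nights and leave nothing to compare with baseline. Families may also change treatment because of how the child is doing, so the remaining set may be informatively selected. The result should be read as a check on the main comparison, not a replacement for it.
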